12.1.4 Discharge

At discharge, assessments will include:

• Postoperative complications rate and severity assessed by Clavien-Dindo grading (62)

Upon discharge, participants will be given information packs which will include:

- Information on the trial follow ups via leaflet (and watch a short animation video if randomised to the intervention arm of the Follow-up SWAT see Section 17)
- Information on the Limbless Association's Volunteer Visitor Scheme, that links patients who have recently undergone MLLA with someone who has lived experience of MLLA and is willing to provide peer-to-peer support.

Many participants will also be supported on discharge by the local 'limb fitting' team, which often includes a psychologist. Some hospitals also have access to inpatient psychologists who can support these participants.

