Immediate postoperative pain management commonly involves epidural or intravenous (IV) patientcontrolled analgesia, which relies on opioid based agents. A recent UK wide National Confidential Enquiry into Patient outcome and Deaths review into lower limb amputations found that strong opioids were the most frequently used type of postoperative analgesia (22). While opioids provide excellent pain relief, they also have many associated side effects, including nausea and vomiting (23), constipation (24), sedation and pruritus (25). Morphine is normally self-administered via a pump, and

Trials Research Canolfan Ymchwil Treialon

Centre for

therefore the patient experiences pain before self-treating. Tolerance, dependence, and addiction to opioids can occur with prolonged use (26,27). The pharmacokinetics of opioids are altered with increasing age, deteriorating renal function and polypharmacy, all of which are common in people with PAD and/or diabetes, leading to unpredictable adverse drug effects and interactions (28). Furthermore, opioid related side effects are problematic, increasing in-hospital costs by 7 to16% and overall length of stay by approximately 10% (29,30). Acute postoperative opioid use costs £23/day/patient (31).

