Given the marked side effects of opioids, the American Society of Anaesthesiologists suggest using multimodal analgesic strategies for managing postoperative pain (32). These include the use of opioid sparing agents (such as nonsteroidal anti-inflammatory drugs, paracetamol, or anticonvulsants) which have been shown to reduce overall inpatient costs compared to opioid analgesia (33). The use of peripheral wound catheters (PWCs) with local anaesthetic infusion is also suggested, where possible. PWCs are thin catheters (epidural catheters are commonly used) that may be placed under direct vision at the time of surgery by the operating surgeon (surgical PWCs), or percutaneously under radiological guidance either pre- or postoperatively (radiological PWCs). Perineural catheters (PNCs) are a specific type of PWC placed adjacent to major nerves, allowing a constant infusion of local anaesthetic directly to the perineural (juxta-neural) space, in addition to the wound locally. Therefore, PNCs may reduce postoperative pain and opioid use (34). In a meta-analysis of randomised controlled trials (RCTs, n = 44, 2141 patients) examining surgical PWCs placed during a variety of surgical procedures, PWC use was associated with a reduction in postoperative pain scores at rest and movement, opioid usage, nausea and vomiting and length of hospital stay, and with an increase in patient satisfaction (35). In general, the risks of PWC use appear low (36) with very low rates of side effects, including infection, occurring with PNC use specifically (37).

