5.4 Secondary Outcomes measures

Secondary outcome measures:

(First 5 postoperative days)

- Participant satisfaction related to pain management during the preceding 24 h, assessed preoperatively and once daily postoperatively for up to five days using a 4-point Likert scale
- Opioid use assessed once daily postoperatively for five days, converted to morphine equivalents using the University of Alberta Multidisciplinary Pain Centre Opioid Conversion Guide (54)
- Opioid side effects (frequency and severity of symptoms) assessed once daily postoperatively for five days

(At discharge)

- Morbidity, assessed using Clavien-Dindo grading at discharge
- Length of hospital stay

(At 30 days)

Surgical site infection rates classified as per the 2008 CDC/NHSN document assessed at 30 days (55)

(At 90 days)

• Days alive and out of hospital assessed at 90 days (DAOH-90)

(At 3 to 6 months)

- Chronic residual limb pain assessed at 3 and 6 months
- Phantom limb pain assessed at 3 and 6 months
- Length of hospital stay assessed at 3 and 6 months
- Residual limb surgery assessed at 30 days, 3 months, and 6 months
- Health-related QoL assessed using EQ-5D-5L at 3 months and 6 months
- Participant reported anxiety and depression assessed using HADS at 3 months and 6 months
- Prosthesis fitting assessed as rate and time to fitting using SIGAM at 3 and 6 months
- Assessment of health care resource usage during the first 6 months postoperatively
- Mortality assessed at 6 months.

6 Trial Design and Setting

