12.1.5 Outcomes Collected at 30 Days

- Surgical site infection, as defined by CDC 2021 (55)
- Delayed **wound healing** of the surgical wound (defined as absence of complete epithelialisation of the wound)
- Residual limb surgery (revision or debridement)

Table 2 Schedule of enrolment, interventions, and assessments

Dat	а Туре	Source Data	Data type	Screening	Baseline/ Pre- operative assessment	At Operation	First 5 Post- operative days	30 days	At discharge	3 Month FU	6 Month FU	Freque ncy	By whom
1	Informed Consent	Consent form, documente d in medical notes	-	X								Once	Qualified practitioner with delegated responsibility
2	Eligibility Assessment	Eligibility form	-	X								Once	Qualified practitioner with delegated responsibility
3	Registration	Registratio n form	-		x							Once	Site research team
4	Demographics	CRF			X							Once	Site research team

Dat	а Туре	Source Data	Data type	Screening	Baseline/ Pre- operative assessment	At Operation	First 5 Post- operative days	30 days	At discharge	3 Month FU	6 Month FU	Freque ncy	By whom
5	Past surgical and medical history	Medical notes and CRF	(inc. smoking history, weightl, and type of diabetes mellitus)		x							Once	Site research team
6	Pre-operative pain	CRF	11-point NRS		x							Once	Participant reported
7	Pre-operative opioid and analgesic use	Medical notes			X							Once	Site Research team
8	Pre-operative blood results, including liver & renal function tests	Medical notes	Routine blood tests		X							Once	Site Research team

Data	а Туре	Source Data	Data type	Screening	Baseline/ Pre- operative assessment	At Operation	First 5 Post- operative days	30 days	At discharge	3 Month FU	6 Month FU	Freque ncy	By whom
9	Review of pre- operative resting 12-lead ECG	Medical notes	ECG		x							Once	Site Research team
10	(For participants of child-bearing potential) Review of pre- operative pregnancy test result	Medical notes	Pregnanc y test result		X							Once	Site Research team
11	Planned level of amputation	Medical notes			X							Once	Site Research team
12	Health services contact in previous 3 months	QRF	Client Service Receipt Inventory (CSRI)		x					X	x	Once	Participant reported / Site Research team

Data	а Туре	Source Data	Data type	Screening	Baseline/ Pre- operative assessment	At Operation	First 5 Post- operative days	30 days	At discharge	3 Month FU	6 Month FU	Freque ncy	By whom
13	Health-related Quality of Life	QRF	EQ-5D-5L and HADS		Х					x	x	Once	Participant reported

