15.1 Main Analysis

For the statistical analysis of the primary outcome (proportion of 'successes' and 'failures' of pain control in the first 5 postoperative days for each participant, as defined in Section 14.3), we will use the intention-to-treat population and fit a multilevel logistic regression model, with the minimisation variables and condition (PAD or diabetes) as fixed-effect covariates and with random centre effects, to test for a difference between treatment arms at a 5% two-sided alpha level. Secondary outcomes will be analysed using similar multilevel regression models depending on the type of outcome (see Table 8) with the same covariate adjustments using the intention-to-treat principle. We will account for possible 'truncation by death' in sensitivity analyses. Additional secondary analyses considering the level of intervention fidelity will also be undertaken, including successful placement of the PNC, the PNC remaining in place for 5 days, and the local anaesthetic being infused within the dose and

rate ranges specified in the protocol for 5 days. All treatment effects will be reported as point estimates with 95% confidence intervals and p-values.

Table 8 Summary of Analysis for Secondary Outcomes

Outcome	Measure	Time frame	Analysis
Average pain	NRS	5d	Linear regression of median or mean (adjusted for baseline)
Overall satisfaction with analgesia	Likert scale	5d	Linear regression of transformed measure (if appropriate)
Total opioid use	Morphine equivalents	5d	Linear regression (adjusted for baseline)
Opioid side effects	Frequency and severity of symptoms	5d	Linear regression of transformed measure (if appropriate)
Surgical site infection	Proportion of people with infection	30d	Logistic regression
Delayed wound healing	Proportion of people with delay	30d, 6m	Logistic regression
Residual limb surgery	Proportion of people with surgery	30d, 6m	Logistic regression
Phantom limb pain	NRS	3m, 6m	Linear regression
Chronic stump pain	NRS	3m, 6m	Linear regression
Health utility/QoL	EQ-5D-5L	3m, 6m	Linear regression of transformed measure (adjusted for baseline)
Depression	HADS	3m, 6m	Linear regression of transformed measure (adjusted for baseline)
Prosthesis fitting	Proportion of people using prosthesis Time to achieve fitting	3m, 6m	Logistic regression Cox regression

Level of independence	SIGAM grading	3m, 6m	(Ordered) logistic regression, tabulation
independence			
Mortality	Proportion of people dead	6m	Logistic regression

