	Time to death		Cox regression
	Cause of death		Tabulation
Hospital stay	Time to discharge	6m	Cox regression
Hospital re-	Proportion of people re-	6m	Logistic regression
admissions	admitted		
DOAH-90	Days alive and out of	90d	Linear regression of transformed
	hospital		measure (if appropriate)
Postoperative	Clavien-Dindo grading	At	(Ordered) logistic regression,
complications		discharge	tabulation
MLLA of	Proportion of people who	6m	Logistic regression
contralateral limb	were a unilateral amputee		
	who subsequently		
	underwent contralateral MLLA.		

A comprehensive SAP will be finalised prior to database lock by the trial statistician, with support from the TMG, and agreed by the TSC.

15.1.1Sub-group and Interim Analysis

No interim analysis is planned. Sub-group analyses may be performed for sex, history of diabetes mellitus, anaesthetic given, type of infusion device used and level of amputation. Any planned sub-group analyses will be agreed by the TMG and pre-specified in the SAP.

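### Clavien-Dindo complications are graded only up to discharge, so time at risk varies with length of stay, which treatment could change

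*Protocol*

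**What the plan says.** Section 12.1.4 (Discharge) lists "Postoperative complications rate and severity assessed by Clavien-Dindo grading (62"). Section 5.4 has the same outcome as "Morbidity, assessed using Clavien-Dindo grading at discharge". The synopsis, the secondary objectives in section 5.2, Table 2 (row 30, recorded once) and Table 8 (time frame: at discharge) all agree. Table 8 plans ordered logistic regression and tabulation, with no term for time at risk. Section 15.1 adds: "All treatment effects will be reported as point estimates with 95% confidence intervals and p-values".

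Two statements in section 4.1 bear on length of stay. Opioid side effects are said to increase "overall length of stay by approximately 10" per cent. A meta-analysis of surgical wound catheters across a variety of procedures is said to show lower "opioid usage, nausea and vomiting and length of hospital stay", and the perineural catheter is described as one type of wound catheter. Table 8 analyses time to discharge and days alive and out of hospital at 90 days as outcomes. Section 14.2 states that the trial is not blinded.

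Related outcomes do have fixed times. Surgical site infection is taken at 30 days, wound healing and residual limb surgery at 30 days and 6 months, and re-admission, contralateral amputation and mortality at 6 months. General SAE reporting ends at postoperative day 7; only serious adverse reactions are reported after that (section 13.5.1).

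**The concern.** The observation window for the overall complication grade closes at an event that comes after randomisation and that the allocated treatment may influence. Discharge decisions are also made by teams who know the allocation. With the same daily risk of complications in both arms, the arm that goes home sooner has less time in which a complication can be seen and graded, so it would tend to show fewer and milder complications.

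The other data collection fills this gap only in part. A cardiac, respiratory, renal or thromboembolic complication after discharge receives no Clavien-Dindo grade. If it leads to re-admission, it enters a yes/no count at 6 months without severity. A statistical analysis plan cannot repair this later, because the grade would not have been collected.

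At stake is the reading of one comparison that is named in the secondary objective and reported with a confidence interval and p-value.

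**Working it through.** **What the protocol supplies.** It gives no complication rate, length of stay or power for this outcome, so there is no stated figure to reproduce. Its sample size, which concerns the primary outcome, does reproduce: 61.7% against 61.7% × 1.2 = 74.04%, 90% power, two-sided 5%, pooled variance, gives 299 per arm, and 598/0.92 = 650. The illustration below uses 650/2 = 325 per arm. Everything else in it is an assumption.

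**Assumptions.**
- The outcome is simplified to any complication, yes or no.
- The true complication hazard is identical in both arms.
- Stay follows a gamma distribution with shape 2 and mean L = 10, 20 or 30 days in the control arm.
- Mean stay is 0, 5, 10 or 20% shorter with the catheter.
- The 30-day risk P30 is 30% or 60%, and K = −ln(1 − P30).
- The cumulative hazard is either constant, H(t) = Kt/30, or early-peaked, H(t) = K(1 − e^(−t/5))/(1 − e^(−6)).

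**Formula.** The probability that a complication is seen before discharge is E[1 − exp(−H(stay))]. With a constant hazard h = K/30 and gamma stay this is 1 − (1 + hL/2)^(−2).

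**Worked case: L = 20, P30 = 60%, stay 10% shorter.** K = 0.9163 and h = 0.03054.
- Control: 1 − (1 + 0.3054)^(−2) = 41.3%.
- Catheter, mean stay 18 days: 1 − (1 + 0.2749)^(−2) = 38.5%.
- Spurious difference 2.8 points, apparent odds ratio 0.888.
- The early-peaked hazard gives 55.2% against 54.5%, odds ratio 0.970.

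**Rejection rate.** With d = difference/SE and SE = √[a(1−a)/325 + b(1−b)/325], the chance of p < 0.05 is 1 − Φ(1.96 − d) + Φ(−1.96 − d). The worked case gives 11.5% with the constant hazard and 5.4% with the early-peaked one.

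**Ranges over all values of L and P30, with no true effect:**

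| Stay shorter by | Hazard | Difference (points) | Odds ratio | Rejection |
|---|---|---|---|---|
| 0% | either | 0 | 1.00 | 5% |
| 5% | constant | 0.5–1.5 | 0.941–0.949 | 5.5–6.7% |
| 5% | early | 0.1–0.6 | 0.975–0.993 | 5.0–5.3% |
| 10% | constant | 1.0–3.1 | 0.883–0.897 | 7.1–12.4% |
| 10% | early | 0.3–1.3 | 0.948–0.986 | 5.1–6.3% |
| 20% | constant | 2.0–6.5 | 0.770–0.795 | 14.0–38.4% |
| 20% | early | 0.6–2.9 | 0.890–0.969 | 5.4–11.6% |

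If the catheter lengthened stay, the sign would reverse. With a common window counted from surgery and events ascertained equally in both arms, equal hazards give an odds ratio of 1.00 and 5% rejection whatever the stay.

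**Scale.** The largest difference in the 10% rows is 53.0% against 49.9%. Its standard error is √(0.530 × 0.470/325 + 0.499 × 0.501/325) = 3.9 points, so the 3.1-point shift is smaller than one standard error.

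**The case against.** A reader might infer from section 4.1 that the protocol expects the catheter to shorten stay, and that the comparison is therefore biased in its favour. The documents do not support that. The evidence on stay comes from wound catheters in mixed surgery, with no size given. The protocol's own review of catheters in amputation reports no length-of-stay result, and it says the reduction in opioid use disappeared when only randomised trials were considered. The 10% figure describes the effect of opioid side effects on stay; it is not a catheter effect, and both arms may receive opioids. It serves here only as one assumed value among several.

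The size may also be small. Infusion lasts at most five days, and if complications cluster early the shift at a 10% difference is 0.3 to 1.3 points. Complications themselves prolong stay, which the illustration ignores. For the same reason, dividing by days in hospital would not be a clean repair.

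Many harms already have fixed windows, serious adverse reactions are reported to the end of follow-up, and the time-to-discharge analysis will show readers whether stay differed. It would therefore be wrong to call this the main safety comparison or to call its result uninterpretable.

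All of this limits direction, size and importance. It does not remove the structural point: the only overall severity grade stops at a participant-specific time that treatment could change.

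**Conclusion.** The point holds as a conditional one. Grading stops at discharge wherever the protocol mentions this outcome, and no fixed-window version exists. The comparison is unbiased on this account if stays are equal, favours the catheter if it shortens stay, and disfavours it if it lengthens stay. The protocol does not establish which of these will occur.

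For a 10% shorter stay and no true effect, the shift is about 1.0 to 3.1 points with a constant hazard and 0.3 to 1.3 points with early clustering. A 20% difference would roughly double this. These figures rest on assumed stays, risks and hazard shapes, on a yes/no simplification of the grade, and on no feedback from complications to stay.

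One named secondary outcome is affected. The primary analysis and the sample size are not. The change is worth making because it is cheap and because ungraded events cannot be recovered at analysis.

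**What to change.** Define the outcome as the worst Clavien-Dindo grade from operation to day 30, in or out of hospital. Collect it at the 30-day medical-note review that site staff already do for surgical site infection, wound healing and residual limb surgery (Table 2, rows 24 to 26). Make that grade the one analysed in Table 8, and keep the to-discharge grade as a supportive, descriptive result. Change sections 5.2, 5.4, 12.1.4 and 12.1.5, the synopsis and Table 2 to match.

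The cost is one more item at an existing review. Two limits should be stated. Events managed outside hospital may be under-recorded in the notes, possibly slightly more in an arm discharged earlier, so the dependence on stay shrinks but may not vanish. In-hospital events after day 30 would appear only in the supportive grade; under the assumed gamma stay with a 20-day mean, e^(−3) × (1 + 3) = about 20% of participants would still be in hospital then. The sample size is unchanged.

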12.1.5 Outcomes Collected at 30 Days

- Surgical site infection, as defined by CDC 2021 (55)
- Delayed **wound healing** of the surgical wound (defined as absence of complete epithelialisation of the wound)
- Residual limb surgery (revision or debridement)

Table 2 Schedule of enrolment, interventions, and assessments

Dat	а Туре	Source Data	Data type	Screening	Baseline/ Pre- operative assessment	At Operation	First 5 Post- operative days	30 days	At discharge	3 Month FU	6 Month FU	Freque ncy	By whom
1	Informed Consent	Consent form, documente d in medical notes	-	X								Once	Qualified practitioner with delegated responsibility
2	Eligibility Assessment	Eligibility form	-	X								Once	Qualified practitioner with delegated responsibility
3	Registration	Registratio n form	-		x							Once	Site research team
4	Demographics	CRF			X							Once	Site research team

Dat	а Туре	Source Data	Data type	Screening	Baseline/ Pre- operative assessment	At Operation	First 5 Post- operative days	30 days	At discharge	3 Month FU	6 Month FU	Freque ncy	By whom
5	Past surgical and medical history	Medical notes and CRF	(inc. smoking history, weightl, and type of diabetes mellitus)		x							Once	Site research team
6	Pre-operative pain	CRF	11-point NRS		x							Once	Participant reported
7	Pre-operative opioid and analgesic use	Medical notes			X							Once	Site Research team
8	Pre-operative blood results, including liver & renal function tests	Medical notes	Routine blood tests		X							Once	Site Research team

Data	а Туре	Source Data	Data type	Screening	Baseline/ Pre- operative assessment	At Operation	First 5 Post- operative days	30 days	At discharge	3 Month FU	6 Month FU	Freque ncy	By whom
9	Review of pre- operative resting 12-lead ECG	Medical notes	ECG		x							Once	Site Research team
10	(For participants of child-bearing potential) Review of pre- operative pregnancy test result	Medical notes	Pregnanc y test result		X							Once	Site Research team
11	Planned level of amputation	Medical notes			X							Once	Site Research team
12	Health services contact in previous 3 months	QRF	Client Service Receipt Inventory (CSRI)		x					X	x	Once	Participant reported / Site Research team

Data	а Туре	Source Data	Data type	Screening	Baseline/ Pre- operative assessment	At Operation	First 5 Post- operative days	30 days	At discharge	3 Month FU	6 Month FU	Freque ncy	By whom
13	Health-related Quality of Life	QRF	EQ-5D-5L and HADS		Х					x	x	Once	Participant reported
14	Randomisation	CRF	-			X						Once	Site Research team
15	Method of anaesthesia	Medical notes and CRF	Surgery CRF			X						Once	Site Research team
16	Pre-operative regional nerve block performed, and drugs used	Medical notes and CRF	Surgery CRF			X						Once	Site Research team
17	Intraoperative nerve management	CRF, documente d in surgical notes	Surgery CRF- Successful identificati on of nerve, method			X						Once	Site Research team

Data	а Туре	Source Data	Data type	Screening	Baseline/ Pre- operative assessment	At Operation	First 5 Post- operative days	30 days	At discharge	3 Month FU	6 Month FU	Freque ncy	By whom
			used to cut nerve and whether it was tied.										
18	Actual level of amputation	Medical notes and CRF	Surgery CRF			X						Once	Site Research team
19	Postoperative pain	CRF	11-point NRS				X					Twice daily	Partcipant reported
20	Overall satisfaction with analgesia	CRF	5-point scale (0 to 4)		X		x					Once daily	Participant reported
21	Total opioid use (converted to morphine equivalents)	Medical notes					Х					Daily	Site Research team

Data	а Туре	Source Data	Data type	Screening	Baseline/ Pre- operative assessment	At Operation	First 5 Post- operative days	30 days	At discharge	3 Month FU	6 Month FU	Freque ncy	By whom
22	Opioid side effects	CRF	Frequency & severity of symptoms				x					Daily	Participant reported
23	(Intervention arm only) Fidelity of nerve catheter usage, specifically duration it remains in place, and duration of delivery of local anaesthetic	CRF	Catheter monitoring CRF				X					Daily	Site Research team
24	Surgical site infection	Medical Notes						X				Once	Site Research team

Data	а Туре	Source Data	Data type	Screening	Baseline/ Pre- operative assessment	At Operation	First 5 Post- operative days	30 days	At discharge	3 Month FU	6 Month FU	Freque ncy	By whom
25	Delayed wound healing	Medical Notes						X			x	Once	Site Research team
26	Residual limb surgery	Medical Notes						X			x	Once	Site Research team
27	Residential status upon discharge	CRF	Discharge form						x			Once	Site Research team
28	Resource use: Additional equipment and home adaptions	CRF	Discharge form						X			Once	Site Research team
29	Inpatient analgesic use	Medical notes							X			Once	Site Research team
30	Postoperative complications	Medical notes/ CRF	Clavien- Dindo grading						X			Once	Site Research team

Data	і Туре	Source Data	Data type	Screening	Baseline/ Pre- operative assessment	At Operation	First 5 Post- operative days	30 days	At discharge	3 Month FU	6 Month FU	Freque ncy	By whom
31	Phantom limb pain		11-point NRS							X	X	Once	Participant reported
32	Chronic stump pain		11-point NRS							Х	X	Once	Participant reported
33	Prosthesis fitting (inc. Time to achieve fitting)		SIGAM							Х	X	Once	Participant reported
34	Level of independence		SIGAM grading							x	x	Once	Participant reported
35	Resource Use (additional operations, consultations)	QRF						X		X	x	Once	Participant reported
36	Length of hospital stay	Medical notes							X		X	Once	Site Research team

Data	а Туре	Source Data	Data type	Screening	Baseline/ Pre- operative assessment	At Operation	First 5 Post- operative days	30 days	At discharge	3 Month FU	6 Month FU	Freque ncy	By whom
37	Hospital re- admissions										x	Once	Site Research team
38	MLLA of contralateral limb										X	Once	Site Research team
39	Mortality (Time, Cause)	Medical notes									X	Once	Site Research team
40	Adverse effects	Medical notes /CRF						As R	equired		L 	1	Site Research team
41	SAEs / SARs	Medical notes /CRF	SAE form					As	Required				Sit Research team
42	Withdrawals	Withdrawal form	-					As	Required				Site Research team and CTR

